13 STUDY PROCEDURES BY VISIT DAY

The following sections describe in detail all study procedures. A flow chart of all study procedures is presented in Table 1. Source documents will be completed at each subject's visit, and the data captured in the source documents will be subsequently entered onto case report forms (CRFs) by the investigator or designee.

13.1 VISIT 1/BASELINE VISIT (STUDY DAY 0)

The following pre-study screening procedures should be completed prior to initiating study treatment:

- 1. Obtain a signed and dated subject informed consent form and authorization to use and disclose medical information prior to performing any study-specific procedures;
- 2. Obtain a signed and dated Photographic Release Form prior to obtaining any photographs
- 3. Collect demographic information including date of birth, sex, race, ethnicity and Fitzpatrick skin type;
- 4. Collect a medical history (only relevant, current/ongoing diseases/conditions and past surgeries/procedures as determined by the investigator);
- 5. Review inclusion and exclusion criteria;
- 6. Upon qualifying for the study, subjects will be assigned a study number (See Section 8.4);
- 7. Conduct Investigator's Skin Grading Assessment, see Section 11.1;
- 8. Obtain photographs. For details instruction on obtaining photographs, see Section 11.2;
- 9. A urine pregnancy test will be performed on females of child-bearing potential.
- 10. Review and record concomitant medications;
- 11. Dispense study product. Complete the product accountability CRF form;
- 12. Instruct subject in the application of the Obagi 360 system and provide written instructions;
- 13. Schedule the next visit with the subject on study Day 14 (\pm 2 days).

13.2 VISITS 2 THROUGH 5 (STUDY DAY 14 [\pm 2 DAYS], AND STUDY DAYS 28, 56, AND 84 [\pm 5 DAYS])

The following procedures will be performed at these visits:

- 1. Conduct Investigator's Skin Grading Assessment, see Section 11.1;
- 2. Obtain photographs. For details instruction on obtaining photographs, see Section 11.2;
- 3. A urine pregnancy test will be performed on females of child-bearing potential at the End of Study Visit.
- 4. Conduct subjects' self-assessment see Section 11.3, Appendix 2 and Appendix 3;
- 5. Assess tolerability of the Obagi 360 system;
- 6. Review and record concomitant medications;
- 7. Review and record adverse events:
- 8. Dispense/collect study product. Complete the product accountability CRF form;
- 9. Review with subject the application of the Obagi 360 system;
- 10. Schedule the next visit with the subject or end subject participation at Visit 5.

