2 PROTOCOL SYNOPSIS

Study Number:	OMP360-01
Title of Study:	An Open-Label Study to Evaluate the Anti-Aging Effects of Three Months of Treatment using the Obagi 360 System in Subjects with Photodamage
Study Center(s):	Up to two study centers in the United States
Study Period:	3Q13 – 2Q14
Objectives:	To observe improvement in the appearance and the effects of the Obagi 360 skincare system when used consistently over a 3 month time period

Methodology: Open-label study of the Obagi 360 system used daily for 3 months to evaluate the effects on photodamage. Subjects will be evaluated at five time points; a baseline visit and at 2, 4, 8, and 12 weeks. The total study duration will be 12 weeks for each subject.

At the baseline visit (Day 1) the subject will complete the informed consent and photo release and will be evaluated for eligibility. Eligible subjects will be assigned a subject number and enrolled. At the baseline visit photographs will be taken and the investigator will complete the skin grading assessment. The subject will be instructed in the use of the product. The Obagi 360 skincare system will be applied once daily.

The subjects will return to clinic on Days 14 (\pm 2 days), and 28, 56, and 84 (\pm 5 days) to assess response. At each visit photographs will be obtained and the investigator will complete the skin grading assessment. Additionally, the subject will complete a self-assessment at subsequent visits.

Number of Subjects: A total of approximately 40 subjects will be enrolled

Inclusion Criteria: Subjects may participate in the study if they meet the following criteria:

- 1. Female subjects between the ages of 25-40
- 2. Fitzpatrick skin type I-IV
- 3. Investigator Assessment of Overall Integrated Facial Photodamage of mild to moderate (score of 2 5 inclusive; Section 11.1) and prone to breakouts (non-inflammatory), as assessed by the investigator.
- 4. Willing to withhold use of all other topical skincare products during the study with the exclusion of facial cleansers and Latisse. Make-up is allowed.
- 5. Willing to withhold all facial treatments during the course of the study including toxins, fillers, microdermabrasion, IPL, peels, facials, laser treatments, tightening treatments. Waxing and threading is allowed but not facial laser hair removal.
- 6. Willing to remove all makeup at every visit for pictures.
- 7. Willing to sign Photo release.
- 8. Willing and able to give written informed consent.

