7.4 DURATION OF SUBJECT PARTICIPATION

The duration of the treatment is daily for 12 weeks. Subjects will be expected to come to the study center for the baseline visit and 4 additional study visits.

Subject's Self-Assessment of improvement Questionnaire (Appendix 2) will only be administered at Visit 2 and Visit 3

Subjects receive instruction during visit on how to apply study treatment product. The first application of study treatment product to the face will be applied at the conclusion of the Baseline visit as part of the Study Treatment Dispensing and Application Training.

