9.4 DOSE ADMINISTRATION

The site will provide instructions for the proper application of Obagi 360 system at baseline (Appendix 1). Study product should be applied by the subject for the subsequent days. The subject will be instructed to use the Exfoliating Cleanser in the morning and in the evening. After the Exfoliating Cleanser is used in the morning, the Moisturizing Cream (0.5% retinol with moisturizers and Hydrafactor SPF 30) will be applied. After the Exfoliating Cleanser is used in the evening, the Night Cream (0.5% retinol with moisturizers) will be applied.

Written instructions for the proper administration of study product will be provided to the subject (Appendix 1).

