11.2 PHOTOGRAPHS

The following instructions will be used to obtain photographs at each visit. Detailed instructions are provided in the Photography Manual.

- 1. Instruct subject to remove all makeup including eye makeup and lipstick.
- 2. Wipe subject's face with make-up remover to remove any residual makeup and apply blotting papers to eliminate shine (both items will be provided by sponsor).
- 3. Clear all hair away from face with headband (provided by sponsor).
- 4. Place white drape over subject's clothes (provided by sponsor).
- 5. Using the Visia camera system (Canfield Scientific), be sure the stool height is adjusted, the subject is sitting up straight and the subject has a neutral, relaxed facial expression with eyes open. Each subject will have a frontal, right oblique, and left oblique picture taken with specified filters: Standards, parallel polarized, perpendicular polarized, UV, fluo and UV spots.
 - For frontal view: subject's chin should be centered and gently resting in the chin cup. The subject's head, neck and spine should be aligned and she should face the booth squarely in the appropriate direction for the view.
 - For right oblique view: position the forehead support and the chin cup on the right side of the device. Have subject rest chin in cup and tilt forward until positioned.
 - For left oblique view: position the forehead support and the chin cup on the left side of the device. Have subject rest chin in cup and tilt forward until positioned.

All images will be captured on a flash drive and sent to the sponsor at the end of the first month of the study, the middle of 2 month of the study and at the end of the study.

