APPENDIX 1: INSTRUCTION FOR APPLICATION OF STUDY PRODUCT

Please follow these instructions carefully. Contact the study staff at the telephone number noted below if you have any questions about the study:

Contact:	Telephone:

Morning Cleansing and Application Day Cream with SPF: once a day in the am (morning)

- STEP 1: Wet face and hands with lukewarm water. Dispense a full 1-pump dose of the Exfoliating Cleanser into the palm of your hand and gently rub over your entire face, taking care to avoid the eyes. Rinse completely with lukewarm water and gently pat your face dry with a towel.
- STEP 2: Using your fingertips, apply a full 1-pump dose of the Moisturizer to the entire face and forehead, avoiding the eye area.

Evening Cleansing and Application Night Cream: once a day in the pm (evening)

- STEP 1: Thoroughly remove all eye makeup. Wet face and hands with lukewarm water.

 Dispense a full 1-pump dose of the Exfoliating Cleanser into the palm of your hand and gently rub over your entire face, taking care to avoid the eyes. Rinse completely with lukewarm water and gently pat your face dry with a towel.
- STEP 2: Using your fingertip, gently a full 1-pump dose of the Night Cream to the entire face and forehead, avoiding the eye area.

For all products, avoid contact with eyes. Rinse eyes thoroughly if contact occurs.

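### Skin preparation and time since last application are not fixed before grading, so a same-day surface effect of the product can enter the change from baseline

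*Protocol*

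**What the plan says.** **Baseline.** Section 13.1 introduces its list, which includes grading (step 7) and photographs (step 8), with "The following pre-study screening procedures should be completed prior to initiating study treatment". Section 7.4 adds: "The first application of study treatment product to the face will be applied at the conclusion of the Baseline visit". The baseline grade is therefore made without study product on the skin.

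**Follow-up.** Section 9.4 states: "After the Exfoliating Cleanser is used in the morning, the Moisturizing Cream (0.5% retinol with moisturizers and Hydrafactor SPF 30) will be applied". Appendix 1, the subject's own instruction sheet, says to "apply a full 1-pump dose of the Moisturizer to the entire face and forehead, avoiding the eye area". Neither makes an exception for visit days. The synopsis describes the regimen differently, without a time of day: "The Obagi 360 skincare system will be applied once daily".

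**Grading.** In Section 13.2 step 1 is "Conduct Investigator's Skin Grading Assessment, see Section 11.1" and step 2 is photographs. Section 11.1 describes a static 0 to 6 visual scale and says nothing about preparing the face. Section 10 requires makeup to be off for visits but does not mention study product.

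**Wipe and blot.** These appear only in Section 11.2, for photographs: "Wipe subject's face with make-up remover to remove any residual makeup and apply blotting papers to eliminate shine".

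**Analysis.** Section 14.2.3 compares each time point with baseline by a paired t-test at two-sided 0.05. Section 7.2 states that the study is open-label, and the synopsis lists no reference therapy.

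**The concern.** A change score is interpretable when both grades are made under the same conditions. Here the baseline face carries no study product, while the follow-up face may carry a layer applied that morning. Several graded features concern the skin surface as seen on the day: Section 11.1 defines loss of texture by grain and smoothness, sallowness as the opposite of radiance, and also scores fine lines and the appearance of pores. Appendices 5 and 6 list dimethicone, glycerin and sodium hyaluronate among the leave-on ingredients, and Appendix 2 allows subjects to answer that improvement was immediate or came within a day. A same-day effect is thus something the protocol itself allows for.

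If there is such an effect, it adds to whatever change builds up over 12 weeks. No control arm carries the same effect, and neither the visit procedures nor the assessment sections call for the time of last application to be recorded. The two parts cannot be separated afterwards, and no analysis plan can supply a time that was never collected. Varying intervals between application and grading would also add noise.

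**Working it through.** **Step 1: conditions at the two gradings**

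| | Baseline | Visits 2 to 5 |
|---|---|---|
| Study product on the face | None (7.4, 13.1) | Possibly that morning's dose (9.4, Appendix 1) |
| Preparation required before grading | Makeup off (10) | Makeup off (10) |
| Wipe and blot | In 11.2, listed after grading | In 11.2, listed after grading |
| Interval from application to grading | Not applicable | Neither fixed nor recorded |

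The asymmetry is in the first row. The order of grading and photographs is the same at every visit and creates no difference by itself.

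**Step 2: how large a shift would matter**

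Section 14.3 states 40 subjects without an effect size, SD or power, so there is no figure of the plan's own to reproduce. Inputs from the protocol: n = 40 (14.3), paired t-test and two-sided 0.05 (14.2.3). Assumed, because the documents give nothing: SD of change 0.6, 0.8 or 1.0 grade; mean shift d from a fresh dose; no lasting effect; complete data.

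The smallest mean change that reaches significance is t(0.975, 39) × SD / √40. With t = 2.023 and √40 = 6.325, this is 0.32 × SD, or 0.19, 0.26 and 0.32 grade for the three SDs.

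The chance of a significant result at one time point for one component comes from the noncentral t distribution with 39 degrees of freedom and noncentrality d × √40 / SD. For d = 0.3 and SD = 0.8, for example, the noncentrality is 0.3 × 6.325 / 0.8 = 2.37, and the chance is 64%.

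| Assumed shift d | SD 0.6 | SD 0.8 | SD 1.0 |
|---|---|---|---|
| 0.05 | 8% | 7% | 6% |
| 0.1 | 18% | 12% | 9% |
| 0.3 | 87% | 64% | 46% |
| 0.5 | >99% | 97% | 87% |

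Both tails are counted. For d = 0.1 and SD = 1.0 the noncentrality is 0.632; the upper tail gives 9.0% and the lower 0.5%, together 9.5% (9.46% before rounding, shown as 9%). The nominal rate is 5%.

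**Step 3: reading the table**

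The range runs from negligible to decisive, and the documents do not say where the product falls. On a whole-number scale, if each affected grade moves by one step, d = 0.1 means a net 4 of 40 subjects graded one step lower (0.1 × 40), and d = 0.5 means 20 of 40. The lower rows need little; the bottom row asks a lot of a single application.

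**The case against.** **The objective is appearance during use.** Section 7 speaks of improvement in appearance when the system is used consistently. A sponsor can fairly say that how the skin looks on a treatment day is part of the intended effect. This stands as a reason not to call the same-day component an error. It does not remove the gap: whichever effect is meant, grades made at an unknown interval after application mix the two in unknown proportion.

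**A reader might infer that the difference necessarily favours the product.** The documents do not support that. Ingredient lists without concentrations do not show a visible effect hours later. Section 12.2 monitors dryness, scaling and erythema, which could worsen a surface grade. The entry criteria set no washout for ordinary moisturizers, so some subjects may be graded at baseline wearing their own, which would shrink the asymmetry. A favourable direction is plausible, no more.

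**A reader might infer that the protocol requires grading on an unwiped face.** The lists in 13.1 and 13.2 are numbered but not declared a sequence. In 13.1 the eligibility review (step 5) precedes the grading (step 7) that inclusion criterion 3 depends on, so strict order cannot be meant. What stands does not depend on order: no section asks for a product-free face before grading.

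**A reader might infer that residual UV filters distort the follow-up photographs.** The face is wiped before photographs, and Section 14 plans no photographic analysis, so this affects no planned result.

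**Other limits.** An uncontrolled open-label study cannot attribute change to the product in any case, so this is one contributor among several. That limits its importance, but it is among the few that can be reduced at almost no cost. Make-up remover may also not take off all product or undo that morning's exfoliation and hydration; this stands and is why the time should be recorded as well.

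**Conclusion.** The point holds as a gap in standardisation. Baseline grading is made without study product, follow-up grading may come hours after the morning dose, and nothing requires a prepared face or records the interval. Any same-day surface effect enters the paired change scores at all four follow-up visits and cannot be separated later. Fine wrinkling, sallowness, texture and pore visibility look most exposed, judging by their definitions in Section 11.1; that is inference, not something the protocol states.

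The size is unknown. Under the assumptions shown, the chance of a significant result with no lasting effect runs from close to the nominal 5% for a shift of 0.05 grade to between 46% and 87% for 0.3, depending on the SD. With neither direction nor size in the documents, this is a cheap improvement rather than a must-fix.

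**What to change.** In Sections 11.1, 13.1 and 13.2, carry out the makeup removal, wipe and blot already described in Section 11.2 before grading, at every visit including Baseline. State a fixed wait between the wipe and grading, the same at all visits. Photographs can follow on the same prepared skin. Add two CRF fields: time of last study-product application and time of grading.

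This needs no change to dosing. Separately, the once-daily wording in the synopsis and the morning-and-evening regimen in Sections 6.1 and 9.4 and Appendix 1 must be reconciled, since they bear on what may be on the face at a visit.

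The cost is a reordering of existing steps, two fields and a short wait at each visit. The observed improvement may be smaller. Because wiping may leave some product behind, the recorded times are needed to examine whether grades vary with the interval since application.

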7.3 SCHEDULE OF STUDY PROCEDURES

A table outlining the schedule of procedures for this study is presented in Table 1.

Table 1 Procedures Flow Chart

PROCEDURES	BASELINE (DAY 0)	DAY 14 (± 2 Days) and DAY, 28, 56, and 84 (± 5 Days)
	Visit 1	Visits 2 through 5
Obtain Informed Consent, HIPAA Authorization	X	
Obtain Photographic Release Form	X	
Review Inclusion/Exclusion Criteria	X	
Review Medical History	X	
Obtain Subject Demographics	X	
Conduct Investigator's Skin Grading Assessment	X	X
Urine Pregnancy Test ¹	X	X
Obtain Photographs	X	X
Conduct Subject's Self-Assessment ²		X
Assign Subject Number	X	
Review Obagi 360 Application ³	X	X
Dispense/Collect Obagi 360 System	X	X
Assess Tolerability		X
Review Concomitant Medications	X	X
Review Adverse Events		X
Review Compliance with Study Procedures		X

UPT obtained on subjects of child bearing potential only.

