8 SELECTION OF STUDY POPULATION

8.1 INCLUSION CRITERIA

Individuals eligible for inclusion in this study must meet all the following criteria:

- 1. Female subjects between the ages of 25-40
- 2. Fitzpatrick skin type I-IV
- 3. Investigator Assessment of Overall Integrated Facial Photodamage of mild to moderate (score of 2 5 inclusive; Section 11.1) and prone to breakouts (non-inflammatory), as assessed by the investigator.
- 4. Willing to withhold use of all other topical skincare products during the study with the exclusion of facial cleansers and Latisse. Make-up is allowed.
- 5. Willing to withhold all facial treatments during the course of the study including toxins, fillers, microdermabrasion, IPL, peels, facials, laser treatments, tightening treatments. Waxing and threading is allowed but not facial laser hair removal.
- 6. Willing to remove all makeup at every visit for pictures.
- 7. Willing to sign Photo release.
- 8. Willing and able to give written informed consent.
- 9. Subject is able to follow study instructions, accessible for treatment and follow-up at the specified time on the specific required study visit days, and likely to complete all study requirements
- 10. Female subjects of child bearing potential agree to take a urine pregnancy test at the Baseline visit, end of the study and when deemed appropriate by Investigator and/or Sponsor. Subjects of childbearing potential is defined as any female who has experienced menarche and who:
 - a. Has not undergone successful surgical sterilization (i.e. hysterectomy or bilateral oophorectomy)

Or

b. Is not post-menopausal (i.e. amenorrhea equal to or greater than 12 consecutive months)

Or

c. Is on hormone replacement treatment (HRT) with a documented serum follicle stimulating hormone (FSH) level of >35mIU/mL

- 11. Be using an acceptable method of contraception throughout the study if they are female of child-bearing potential. Acceptable methods of birth control include: oral and other systemic contraceptives, double barrier, bilateral tubal ligation, partner vasectomy and abstinence. Oral and other systemic contraceptives must be stable for three months prior to the Baseline visit. Patients on oral contraceptives agree not to alter their oral contraceptive, including dose or regimen for the duration of the study

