9.2.2 DISPENSING

The principal investigator or appropriate designee at each site will be responsible for dispensing the Obagi 360 system to the subjects. At baseline, Day 28 and Day 56 visits, the subject will receive a new Obagi 360 system for the following month's use. At the Day 28, 56 and 84 visits, the subject will return the unused portion of the previous month's supply to the site.

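### Table 1 and Section 13.2 give different pregnancy-test schedules after baseline, and no text says which controls; state one, preferably with tests before the Day 28 and Day 56 dispensing

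*Protocol*

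**What the plan says.** **Table 1 (Section 7.3)** marks the urine pregnancy test at baseline and again in the single column that covers Days 14, 28, 56 and 84. The footnote to that row restricts who is tested, not when: "UPT obtained on subjects of child bearing potential only". Another Table 1 note does restrict by visit: the questionnaire on self-assessed improvement "will only be administered at Visit 2 and Visit 3".

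**Section 13.2, step 3**, in the list for Visits 2 through 5, reads: "A urine pregnancy test will be performed on females of child-bearing potential at the End of Study Visit".

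**Inclusion criterion 10** (Section 8.1, repeated in the synopsis) has subjects of child-bearing potential "agree to take a urine pregnancy test at the Baseline visit, end of the study and when deemed appropriate by Investigator and/or Sponsor".

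**Section 13** says that its subsections describe all procedures in detail, and adds: "A flow chart of all study procedures is presented in Table 1". It does not rank the two.

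**Section 13.1** opens its baseline list with "The following pre-study screening procedures should be completed prior to initiating study treatment". The pregnancy test is step 9 and dispensing is step 11.

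**Section 9.2.2** fixes supply: "At baseline, Day 28 and Day 56 visits, the subject will receive a new Obagi 360 system".

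**Section 12.1.4** requires product to be withheld when pregnancy is suspected on treatment, until a urine test result is known, and stopped for good if pregnancy is confirmed.

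**The concern.** A site cannot tell from the protocol whether to test at Days 14, 28 and 56. Section 15.6 requires compliance with every term and documentation of every deviation. Yet a Day 28 visit without a test is compliant under Section 13.2 and a missed procedure under Table 1. With up to two centers, the sites could follow different schedules.

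The safety side is narrower. Under Section 13.2 the only scheduled test after baseline falls at the last visit, where the site is to "Schedule the next visit with the subject or end subject participation at Visit 5". By then the result can no longer prevent exposure within the study. The supplies at Days 28 and 56 are issued without a scheduled test. For a pregnancy that nobody suspects, the discontinuation rule in Section 12.1.4 would depend on an ad hoc test.

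**Working it through.** The plan gives no figure of its own to reproduce. The check compares the texts and counts tests and intervals.

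**Inputs from the protocol.** 40 subjects (Section 14.3). Visits at Days 0, 14, 28, 56 and 84, with windows of ±2 days at Day 14 and ±5 days at the later visits (Table 1, Section 13.2). Dispensing at Days 0, 28 and 56 (Section 9.2.2).

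**Assumptions not in the protocol.** All 40 subjects are of child-bearing potential and complete. Pregnancy rate 1% to 9% per woman-year. Share of pregnancies that go unsuspected 10% to 50%.

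**Step 1, scheduled tests (discretionary tests excluded).**

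| Schedule | Test days | Per subject | × 40 |
|---|---|---|---|
| Table 1, read literally | 0, 14, 28, 56, 84 | 5 | 200 |
| Section 13.2 with baseline | 0, 84 | 2 | 80 |
| Preferred schedule | 0, 28, 56, 84 | 4 | 160 |

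The two texts differ by 200 − 80 = 120 tests. The preferred schedule adds 160 − 80 = 80 to Section 13.2 and has 200 − 160 = 40 fewer than Table 1.

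**Step 2, supplies issued at a visit with no scheduled test.** Total supplies are 3 × 40 = 120. Under Section 13.2, those at Days 28 and 56 have none: 2 × 40 = 80 of 120. Under Table 1 or the preferred schedule it is 0 of 120.

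**Step 3, longest interval between scheduled tests.** Visit windows are Days 12–16, 23–33, 51–61 and 79–89.

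- Section 13.2: 84 − 0 = 84 days; with windows 89 − 0 = 89.
- Table 1: 28 days; with windows max(16 − 0, 33 − 12, 61 − 23, 89 − 51) = max(16, 21, 38, 38) = 38.
- Preferred: 28 days; with windows max(33 − 0, 61 − 23, 89 − 51) = 38.

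**Step 4, what Day 28 and Day 56 tests could catch.**

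- Exposure: 40 × 84 / 365.25 = 9.2 woman-years.
- Expected pregnancies: 9.2 × 0.01 = 0.092 to 9.2 × 0.09 = 0.828.
- Unsuspected: 0.092 × 0.10 = 0.009 to 0.828 × 0.50 = 0.41.
- Conceptions after Day 56 are out of reach, so at most 56/84 of these count: 0.0092 × 56/84 = 0.006 to 0.414 × 56/84 = 0.28.

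The last range is an upper limit, because a urine test turns positive only some time after conception.

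**The case against.** The strongest reply is that the protocol already points one way. Criterion 10 appears in two places and, like Sections 13.1 and 13.2, schedules tests at baseline and end of study. Only a mark in a pooled column suggests more. That column is demonstrably loose: it also marks dispensing and collection for Visits 2 through 5, whereas Section 9.2.2 provides for neither at Day 14. Specific wording would normally prevail over such a mark. This stands as evidence of likely intent. It does not remove the contradiction, since no rule of precedence is given and the test row carries no visit limit although the questionnaire row does.

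A reader might infer that Table 1 is the true schedule and that Section 13.2 wrongly drops tests. The documents do not support that, for the reasons just given.

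A reader might also infer that the protocol requires a test before each supply. It does not. The baseline test belongs to screening, and the rule in Section 12.1.4 is triggered by suspicion and not tied to dispensing. A schedule of Days 0, 28, 56 and 84 with a negative-result condition is stated nowhere, so it is a recommendation. Nor are subjects unprotected under Section 13.2: contraception is required, subjects are told to report suspicion at once, product is then withheld, and discretionary tests are allowed.

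**Conclusion.** The contradiction holds: five scheduled tests per subject under Table 1 read literally, against two under Section 13.2 and criterion 10. It should be corrected because it concerns a participant-safety procedure and leaves sites unable to know what compliance means. The 120-test difference is a maximum, resting on the literal reading of Table 1 and on all 40 subjects being of child-bearing potential and completing.

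Testing before the Day 28 and Day 56 supplies is a cheap improvement, not the only correct reading. It lets the stop rule act before re-supply, at visits that Table 1 already marks. The gain is small, at most about 0.006 to 0.28 unsuspected pregnancies, and that range depends wholly on assumed rates. Suspicion-triggered testing remains the main control. Nothing here is a claim about the product's reproductive risk, and no efficacy result is affected.

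**What to change.** State one schedule in Table 1 footnote 1, Section 13.2 step 3, and criterion 10 in both Section 8.1 and the synopsis.

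**Preferred wording:** *Subjects of child-bearing potential have a urine pregnancy test at baseline; at Day 28 and Day 56, before new product is dispensed; at Day 84/End of Study; and whenever the investigator or sponsor considers it appropriate.* Add a matching line to Section 9.2.2: *At Day 28 and Day 56, new product is dispensed to these subjects only after a negative result.* Day 14 is left out because no new product is issued then.

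**Cost:** wording in five places and at most 80 urine tests more than Section 13.2 requires (2 × 40), all at visits already scheduled.

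**Minimum correction, if Section 13.2 was intended:** limit Table 1 footnote 1 to baseline and End of Study, plus tests deemed appropriate. This is one edit with no added tests. It removes the contradiction but leaves the 84-day interval.

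Either change is an amendment that needs written approval from the IRB and the sponsor under Section 15.7.
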